11.4.2 Clinical Laboratory Assessments

Blood and urine samples will be analyzed at a local or central laboratory. As described below, urine pregnancy tests will either be analyzed by the site or at home using a home kit. All blood samples will be collected while subjects are in a seated or supine position. Specific instructions for the collection, processing, and shipment of samples will be provided in a separate Laboratory Manual.

Laboratory test results that are abnormal and considered clinically significant will be reported as AEs (see Section 13.1).

The safety laboratory test panels are shown in [Table 11-1](#).

Table 11-1 Safety Laboratory Test Panels

Serum Chemistry	Hematology	Urinalysis^a
Glucose	Hemoglobin	Leukocyte esterase
Blood urea nitrogen ^b	Erythrocytes	Nitrite
Creatinine	Mean corpuscular volume	Urobilinogen
Sodium	Platelets	Urine protein
Potassium	Reticulocytes	pH
Calcium	Leukocytes	Urine blood
Chloride	Differential (absolute and percent):	Specific gravity
Magnesium	Eosinophils	Urine ketones
Bicarbonate	Basophils	Urine bilirubin
Phosphate	Neutrophils	Urine glucose
Total bilirubin, direct bilirubin, indirect bilirubin	Lymphocytes	
Alkaline phosphatase	Monocytes	
Aspartate transaminase	Coagulation	
Alanine transaminase	Activated partial thromboplastin time	
Amylase	Prothrombin time	
Lipase	Prothrombin time International	
Gamma-glutamyl transferase	Normalized Ratio	
Protein		
Albumin		
Creatine kinase		
Cholesterol		

^a If urinalysis results are positive for leukocyte esterase, nitrite, protein, or blood, microscopic examination of urine will be done, and results will be provided for leukocytes, erythrocytes, crystals, bacteria, and casts.

^b If blood urea nitrogen cannot be collected, urea may be substituted.

Pregnancy (β -human chorionic gonadotropin) Tests for all Female Subjects: All female subjects must have a serum pregnancy test at screening. Serum pregnancy tests will be performed at the by site medical staff or a home health nurse and analyzed at the central laboratory. Urine pregnancy tests will either be performed and analyzed at the site or at home by using a home kit provided by the site/home health nurse. Results will be reported to the site by telephone. The urine pregnancy test on Day 1 must be negative before the first dose of study drug is administered to the subject. Additional pregnancy tests may be required according to local regulations and/or requirements.

CF genotype (Screening Period only): CF genotyping will be performed on all subjects to confirm the genotype documented in the subject's medical record.

Additional Evaluations: Additional clinical laboratory evaluations will be performed at other times if judged to be clinically appropriate.

For purposes of study conduct, only laboratory tests done in the central laboratory may be used. Local laboratories may be used at the discretion of the local investigator for management of urgent medical issues. If a local laboratory test value is found to be abnormal and clinically significant, it will be verified by the central laboratory as soon as possible after the investigator becomes aware of the abnormal result. If it is not possible to send a timely specimen to the central laboratory (e.g., the subject was hospitalized elsewhere), the investigator may base the assessment of an AE on the local laboratory value.

11.4.3 Physical Examinations and Vital Signs

A physical examination (PE) of all body systems and vital signs assessment will be performed at screening and select study visits. At other visits, symptom-directed PEs and symptom-directed vital signs assessments can be performed at the discretion of the investigator or healthcare provider.

A PE includes a review of the following systems: head, neck, and thyroid; eyes, ears, nose, and throat (EENT); respiratory; cardiovascular; lymph nodes; abdomen; skin; musculoskeletal; and neurological. Breast, anorectal, and genital examinations will be performed when medically indicated. After screening, any clinically significant abnormal findings in PEs will be reported as AEs.

Vital signs include blood pressure (systolic and diastolic), temperature, pulse rate, and respiration rate. The subject will be instructed to rest for at least 5 minutes before vital signs are assessed.

Arterial oxygen saturation by pulse oximetry will be assessed following at least a 5-minute rest and before study drug dosing. Pulse oximetry will be collected before study drug dosing.

11.4.4 Electrocardiograms

Twelve-lead ECGs will be performed as indicated in [Table 3-1](#) and [Table 3-2](#). Additional 12-lead ECGs will be performed at any other time if clinically indicated. The performance of all ECGs will adhere to the following guidelines:

- The ECG will be done before any other procedures that may affect heart rate, such as blood draws.
- The subject will be instructed to rest for at least 5 minutes before having an ECG.
- The test should be performed in the supine position

ECG traces will undergo safety review by the investigator and be maintained with source documentation. Clinically significant ECG abnormalities occurring during the study through the Safety Follow-up Visit will be recorded as AEs.

To ensure safety of the subjects, a qualified individual at the study site will make comparisons to baseline measurements. If the QTcF is increased by >60 msec from the baseline or an absolute QTcF value is ≥ 500 msec for any scheduled ECG, 2 additional ECGs will be performed approximately 2 to 4 minutes apart to confirm the original measurement. If either of the QTcF values from these repeated ECGs remains above the threshold value (>60 msec from baseline or ≥ 500 msec), a single ECG will be repeated at least hourly until QTcF values from 2 successive ECGs fall below the threshold value that triggered the repeat measurement.

11.4.5 Ophthalmologic Examination

Ophthalmologic examinations will be conducted only for subjects who are <18 years of age on the date of informed consent. The examination does not need to be completed if there is documentation of bilateral lens removal for the subject.

All examinations will be conducted by a licensed ophthalmologist or optometrist and will include:

- measurement of best-corrected distance visual acuity of each eye; and
- pharmacologically dilated examination of the lens with a slit lamp.

The screening examination does not need to be conducted if there is documentation of an examination meeting the protocol requirements that was conducted within 3 months before the date of informed consent.

In addition to the screening ophthalmologic examination, subjects who are <18 years of age on the date of informed consent and who have completed at least 12 weeks of study drug treatment will have a single follow-up ophthalmologic examination. This examination should be completed at or up to 4 weeks before the Week 48 Visit, unless the subject prematurely discontinues study drug, in which case this examination should occur by the Safety Follow-up Visit (or ETT Visit for subjects who do not complete a Safety Follow-up Visit), as described in [Table 3-2](#).

Any clinically significant abnormal findings will be reported as AEs.

11.4.6 Contraception and Pregnancy

The effects of ELX monotherapy or in combination with TEZ/IVA on conception, pregnancy, and lactation in humans are not known. ELX, TEZ, and IVA did not show genotoxic potential in a standard battery of in vitro (Ames test, chromosomal aberration, or micronucleus in cultured mammalian cells) and in vivo (rodent micronucleus) studies. Reproductive toxicology studies of ELX, TEZ, and IVA have not shown teratogenicity in rats and rabbits.

11.4.6.1 Contraception

Contraception requirement for a couple is waived for the following:

- True abstinence for the subject, when this is in line with the preferred and usual lifestyle of the subject. Periodic abstinence (e.g., calendar, ovulation, symptothermal, postovulation methods) and withdrawal are not acceptable methods of contraception. True abstinence must be practiced from the Screening Visit through 90 days after the last dose of study drug.
- If the male is infertile (e.g., bilateral orchiectomy). If a male subject is assumed to have complete bilateral absence of the vas deferens, infertility must be documented before the first dose of study drug (e.g., examination of a semen specimen or by demonstration of the absence of the vas deferens by ultrasound).
- If the female is of non-childbearing potential. To be considered of non-childbearing potential, the female must meet at least 1 of the following criteria:
 - o Postmenopausal: Amenorrheic for at least 12 consecutive months and a serum FSH level within the laboratory's reference range for postmenopausal females
 - o Documented hysterectomy or bilateral oophorectomy/salpingo-oophorectomy

Note: All other females (including females with tubal ligations) will be considered to be of childbearing potential.

- Same-sex relationships

For subjects for whom the contraception requirement is not waived, study participation requires a commitment from the subject that at least 1 acceptable method of contraception is used as a couple. Methods of contraception must be in successful use from signing of consent approximately 28 days before the first dose of study drug (unless otherwise noted), and until 90 days following the last dose of study drug. Additional contraception requirements may need to be followed according to local regulations and/or requirements. Acceptable methods of contraception are listed in [Table 11-2](#).

Table 11-2 Acceptable Methods of Contraception

	Male Subjects and Their Female (Non-study) Partners	Female Subjects and Their Male (Non-study) Partners
Vasectomy performed at least 6 months previously, with a documented negative postvasectomy semen analysis for sperm	Yes	Yes
Bilateral tubal occlusion (e.g., ligation) performed at least 6 months previously	Yes	Yes
Male or female condom with or without spermicide ^a	Yes	Yes
Female barrier contraception (such as diaphragm, cervical cap, or sponge) with spermicide	Yes	Yes
Continuous use of an intrauterine device for at least 90 days before the first dose of study drug	Yes	Yes
Oral, implanted, injected, or vaginal hormonal contraceptives, if successfully used for at least 60 days before the first dose of study drug	Yes	Yes

^a A female condom cannot be used with a male condom due to risk of tearing.

Additional notes:

- If over the course of the study the subject meets the criteria for waiving the contraception requirements, the subject does not need to follow the contraceptive methods listed in [Table 11-2](#).
- Male subjects must not donate sperm during the period starting from the first dose of study drug until 90 days after the last dose of study drug.
- Female subjects should not nurse a child during the period starting from the first dose of study drug until 90 days after the last dose of study drug.
- For male subjects with a female partner of childbearing potential, the couple should not plan to become pregnant during the study or within 90 days after the last dose of study drug, with the exception of couples who plan to become pregnant by artificial insemination using sperm banked by the male subject before the first dose of study drug or sperm from another source.

11.4.6.2 Pregnancy

Subjects will be counseled to inform the investigator of any pregnancy that occurs during study treatment and for 90 days after the last dose of study drug.

If a female subject becomes pregnant during study participation, study drug will be permanently discontinued immediately. The investigator will notify the medical monitor and Vertex GPS

within 24 hours of the site's knowledge of the subject's (or partner's) pregnancy using the Pregnancy Information Collection Form. Male subjects with female partners who become pregnant during the study must use a male condom to avoid exposure of a potential embryo or fetus to study drug via the seminal fluid.

The subject or partner will be followed until the end of the pregnancy and the infant will be followed for 1 year after the birth, provided informed consent is obtained. A separate ICF will be provided to explain these follow-up activities. Pregnancy itself does not constitute an AE.

12 STATISTICAL ANALYSIS

12.1 Sample Size and Power

The primary efficacy endpoint is change from baseline in 2-hour blood glucose levels following an OGTT to the average of Week 36 and Week 48. The primary null hypothesis to be tested is that the mean change from baseline in 2-hour blood glucose levels following OGTT to the average of Week 36 and Week 48 is equal to zero.

Assuming a within group SD of 45 mg/dL and a 10% dropout rate at Week 48, a sample size of 60 subjects will have more than 95% power to detect a mean decrease from baseline of -30 mg/dL in 2-hour blood glucose levels post-OGTT to the average of Week 36 and Week 48, based on a 2-sided, 1-sample *t*-test at a significance level of 0.05 using the EAST software Version 6.4.

12.2 Analysis Sets

The following analysis sets are defined: All Subjects Set, Full Analysis Set (FAS), and Safety Set.

The **All Subjects Set** will include all subjects who were enrolled. This analysis set will be used for all individual subject data listings and disposition summary tables, unless otherwise specified.

The **Full Analysis Set (FAS)** is defined as all enrolled subjects who carry the intended CFTR allele mutation and have received at least 1 dose of study drug. The FAS is to be used in efficacy analyses.

The **Safety Set** is defined as all subjects who have received at least 1 dose of study drug. The Safety Set is to be used for all safety analyses.

12.3 Statistical Analysis

This section presents a summary of the principal features of the planned statistical analyses. Statistical analysis details will be in the statistical analysis plan (SAP) which will be finalized before clinical database lock.

12.3.1 General Considerations

All individual subject data for subjects will be presented in individual subject data listings.

Continuous variables will be summarized using the following descriptive summary statistics: the number of subjects (n), mean, SD, median, minimum value (min), and maximum value (max).

Categorical variables will be summarized using counts and percentages.

Baseline value, unless specified otherwise, will be defined as the most recent non-missing measurement (scheduled or unscheduled) collected before the first dose of study drug. The baseline 2-hour blood glucose level from OGTT will be the average of measurements at screening and Day 1.

Change (absolute change) from baseline will be calculated as Post-baseline value – Baseline value.

Relative change from baseline will be calculated and expressed in percentage as 100% × (Post-baseline value – Baseline value)/Baseline value.

Treatment-emergent (TE) Period will include the time from the first dose of study drug to 28 days after the last dose of study drug or to the completion of study participation (as defined in Section 9.1.6), whichever occurs first.

Incomplete/missing data will not be imputed, unless specified otherwise.

12.3.2 Background Characteristics

Subject disposition, e.g., completed treatment, prematurely discontinued the treatment and the reason for discontinuation, will be summarized.

Demographic and baseline characteristics will be summarized.

Medications used will be coded using the World Health Organization-Drug Dictionary (WHO-DD) and summarized descriptively. Exposure to study drug in (i.e., duration of treatment) and dosing compliance (i.e., percentage of days being compliant to treatment) will be summarized descriptively.

Important protocol deviations will be provided in an individual subject data listing, and summarized, as appropriate.

Additional details will be provided in the SAP.

12.3.3 Efficacy and Pharmacodynamic Analysis

12.3.3.1 Analysis of Primary Efficacy Endpoint

The primary analysis will be based on a mixed-effects model for repeated measures (MMRM) with change from baseline in 2-hour post-OGTT blood glucose levels at Weeks 24, 36, and 48 as the dependent variable. The model will include visit as a fixed effect, and will be adjusted for main covariates as appropriate. The primary result obtained from the model will be the estimated mean change from baseline to the average of Week 36 and Week 48. The estimated change at each visit and the mean change to the average of Week 36 and Week 48 along with the 2-sided 95% CI and *P* value will be provided.

Additional details will be provided in the SAP.

12.3.3.2 Analysis of Secondary Efficacy Endpoints

The secondary endpoints include:

- Proportion of subjects with improvement in dysglycemia categorization (CFRD, IGT, NGT) at Week 48

The number and proportion of subjects with and without response at Week 48 defined as improvement in baseline dysglycemia categorization (i.e. CFRD at baseline to IGT/NGT based

on Week 48 OGTT measurement and IGT at baseline to NGT based on Week 48 OGTT measurement) will be presented. The 2-sided 95% Clopper-Pearson CI on the proportion of responders will also be presented.

Additional details will be provided in the SAP.

12.3.3.3 Multiplicity Adjustment

No multiplicity adjustment is planned.

12.3.3.4 Missing Data Handling

For the primary analysis of the primary endpoint, missing data will be assumed to be missing at random conditional on the observed data and covariate; consequently, no imputation of missing data will be performed.

12.3.3.5 Analysis of Other Efficacy Endpoints

Descriptive statistics will be provided for all other efficacy endpoints based on the FAS.

For the following endpoints, observed values and absolute change from baseline will be summarized:

- SwC1
- BMI
- Body weight
- HbA1c and fructosamine
- Insulin use (dose) in subjects using insulin
- Post-OGTT diabetes-related biomarkers (including insulin, C-peptide, glucagon, calculated indices of insulin secretion [insulinogenic index], and insulin resistance [HOMA-IR])
- Biomarkers of inflammation (including CRP)
- Biomarkers of pancreatic function (including FE-1 and serum IRT)
- Post-OGTT incretin levels (including GLP-1 and GIP)
- Percent of time spent in target blood glucose range of ≥ 70 to < 140 mg/dL (≥ 3.89 to < 7.77 mmol/L) as measured by 7-day CGM in subjects with CFRD
- Selected CGM parameters (including but not limited to percent of time spent between ≥ 140 and < 200 mg/dL [≥ 7.77 and < 11.10 mmol/L], percent of time spent ≥ 200 mg/dL [≥ 11.10 mmol/L], and MAGE) in subjects with CFRD

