- Change from baseline in selected CGM parameters (including but not limited to percent of time spent between ≥ 140 and < 200 mg/dL [≥ 7.77 and < 11.10 mmol/L], percent of time spent ≥ 200 mg/dL [≥ 11.10 mmol/L], and maximum amplitude of glucose excursions [MAGE]) in subjects with CFRD at Week 48.

Number of Subjects Approximately 60 subjects will be enrolled, of whom approximately 30 subjects will have IGT and 30 subjects will have CFRD.

Study Population Male and female subjects with CF who are 12 years of age or older, heterozygous for the *F508del* mutation and an MF mutation (F/MF genotypes), with abnormal glucose tolerance as determined by OGTT at screening (classified as either IGT or CFRD). Among all subjects, approximately 50% may be enrolled while using insulin (≤ 0.3 units/kg/day).

Investigational Drug **Active substance:** ELX (VX-445)/TEZ (VX-661)/IVA (VX-770)
Activity: CFTR correctors (ELX and TEZ) and potentiator (IVA)
Strength and route of administration: ELX 100-mg/TEZ 50-mg/IVA 75-mg fixed-dose combination (FDC) tablets, oral

[figure not shown]
Active substance: IVA (VX-770)

Activity: CFTR potentiator

Strength and route of administration: 150-mg tablets, oral

Study Duration Excluding the Screening Period, the total study duration is approximately 52 weeks (48 weeks for the Treatment Period, and 4 weeks for the Safety Follow-up Period).

Study Design This is a Phase 3b, open-label study in CF subjects 12 years of age and older with F/MF genotypes and abnormal glucose tolerance. A schematic of the study design is shown in [Figure 2-1](#).

Figure 2-1 VX19-445-117 Study Design

ELX: elexacaftor; CFRD: CF-related diabetes; CGM: continuous glucose monitoring; IVA: ivacaftor; N: total sample size; TEZ: tezacaftor

- ^a On Day -7, a CGM sensor will be inserted subcutaneously to assess baseline blood glucose levels for 7 days prior to the first dose of study drug in subjects with CFRD.
- ^b Subjects who complete the visits in the Treatment Period, regardless of whether they are on a treatment interruption, will be offered the opportunity to enroll in an open-label extension safety study evaluating ELX/TEZ/IVA. The Safety Follow-up Visit is not required for subjects who complete the Week 48 Visit and have enrolled in an open-label study within 28 days after the last dose of study drug.

Subjects will receive ELX 200 mg once daily (qd)/TEZ 100 mg qd/IVA 150 mg every 12 hours (q12h).

Assessments Efficacy and PD:

- 2-hour OGTT
- SwCl
- BMI

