9.4 Study Restrictions

Table 9-1 lists prohibited medications. A non-exhaustive list of study prohibitions and cautions for medication will be provided in the Study Reference Manual.

Table 9-1 Prohibited Medications

Medication	Timing of Restriction		Rationale
	Start of Restriction	End of Restriction	
Moderate and strong CYP3A inducers	None allowed within 14 days before the first dose of the study drug on Day 1	None allowed through completion of study participation	ELX, TEZ, and IVA are metabolized extensively via CYP3A4. Therefore, use of moderate and strong inducers and inhibitors of CYP3A, which have the potential to alter the exposure of ELX, TEZ, or IVA, are prohibited.
Moderate and strong CYP3A inhibitors (except ciprofloxacin) ^a	None allowed within 14 days before the first dose of the study drug on Day 1	None allowed through completion of study participation	
CFTR modulators (investigational or approved), except for study drugs	None allowed within 28 days before the first dose of the study drug on Day 1	None allowed until after the last dose of study drug	These agents may confound the results of this study.
Anti-diabetic medications, except for exogenous (subcutaneously injected) insulins	None allowed within 28 days before the first dose of the study drug on Day 1	None allowed until after the last dose of study drug	These agents may confound the results of this study.

CYP: cytochrome P450; ELX: elexacaftor; IVA: ivacaftor; TEZ: tezacaftor

^a Ciprofloxacin is not a moderate CYP3A inhibitor on the basis of results of a drug-drug interaction study conducted with IVA, a sensitive CYP3A substrate (Kalydeco [ivacaftor] US Package Insert).

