11.3 Efficacy and Pharmacodynamics

11.3.1 Oral Glucose Tolerance Test

OGTT will be performed to assess 2-hour glucose levels. Depending on a subject's weight, 1.75 g/kg of body weight or 75 g maximum of oral glucose solution will be administered in the morning after at least 8 hours of fasting (except water and allowed medications other than prednisone and prednisolone). Investigators must counsel subjects on the safe withholding of insulins prior to each OGTT. Insulin use in the 24 hours prior to each OGTT will be recorded by the site.

Blood samples will be obtained at 0, 30 (± 5), 60 (± 5), 90 (± 5), and 120 (± 5) minutes after the start of ingestion of glucose solution. The 0-minute blood sample should be collected immediately prior to ingestion of glucose solution. During study visits with OGTTs, a blood sample will be collected post-OGTT to measure diabetes-related blood biomarkers, including insulin, C-peptide, glucagon, calculated indices of insulin secretion (insulinogenic index), and insulin resistance (HOMA-IR), and to measure incretin levels, including GLP-1 and GIP.

Specific instructions will be provided in the Laboratory Manual

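### Insulin, HOMA-IR and the insulinogenic index are summarised over the whole FAS with no split by insulin use, so a change in injected dose can read as a change in insulin level or resistance

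*Protocol*

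**What the plan says.** Protocol 12.3.3.5 sets the population for this group of endpoints: "Descriptive statistics will be provided for all other efficacy endpoints based on the FAS". The list that follows includes "Post-OGTT diabetes-related biomarkers (including insulin, C-peptide, glucagon, calculated indices of insulin secretion [insulinogenic index], and insulin resistance [HOMA-IR", with observed values and absolute change to be summarised. Protocol 12.2 defines the FAS as "all enrolled subjects who carry the intended CFTR allele mutation and have received at least 1 dose of study drug", so insulin use plays no part in membership.

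On insulin itself:

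- The Synopsis says "Among all subjects, approximately 50% may be enrolled while using insulin (≤ 0.3 units/kg/day" at entry.
- Table 9-1 (Protocol 9.4) bans "Anti-diabetic medications, except for exogenous (subcutaneously injected) insulins", so subcutaneous insulin may continue on study.
- Protocol 11.3.1 requires counselling on withholding insulin before each OGTT, without stating a duration, and adds: "Insulin use in the 24 hours prior to each OGTT will be recorded by the site".
- The list in 12.3.3.5 does use subsets elsewhere. The dose endpoint is "Insulin use (dose) in subjects using insulin", and the CGM items are limited to subjects with CFRD. The insulin-based measures carry no such limit or split.

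In the SAP, insulin use at baseline (Yes/No) is a descriptive characteristic in 8.2.2. The OGTT validity rule in 8.3.1.1 concerns fasting only. Section 8.5 sends the post-OGTT biomarkers to a separate document, which is not among those reviewed.

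**The concern.** HOMA-IR and the insulinogenic index are read as properties of the subject: resistance to, and secretion of, the subject's own insulin. That reading needs the measured insulin to be endogenous. In a subject who injects, the sample may hold both sources, and a pooled mean does not separate them.

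The possible confounder is itself followed as an endpoint (change in insulin dose at Week 48), and there is no control arm. If injected dose changes during the study, measured insulin and HOMA-IR could move with it while secretion and resistance stay the same. Protocol 5.2 names impaired insulin secretion as the primary deficiency, and 9.3.4 describes these markers as mechanistic. The interpretation at stake is whether the subject's own insulin physiology changed.

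The sponsor has seen the general problem. The Protocol's summary of changes gives possible confounding of the OGTT as the reason for adding the 24-hour insulin record. No stated analysis then uses that record.

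**Working it through.** **Plan's own figure.** The plan gives no figure on this point. Its only computed figure is the power for the primary endpoint. A two-sided one-sample t-test with 60 × 0.9 = 54 subjects, a difference of 30 mg/dL, SD 45 mg/dL and alpha 0.05 gives 99.8%, in line with the stated figure of more than 95%. Nothing below depends on it.

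**Inputs from the documents.** N is about 60. The share of users at entry is about 50%, so about 0.5 × 60 = 30 subjects.

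**Assumptions, none in the documents.**

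- Some injected insulin remains at sampling, and the assay detects it.
- HOMA-IR is fasting insulin × fasting glucose / 405, with glucose in mg/dL.
- Endogenous insulin and glucose do not change.
- Users and non-users have the same mean HOMA-IR at baseline. Otherwise *s* below is the users' share of total HOMA-IR, not their share of subjects.

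**Formula.** Let *r* be the injected share of measured fasting insulin in users, *c* the relative change in injected insulin and *s* the share of users. With glucose fixed, HOMA-IR is proportional to total insulin, so the spurious change is:

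- among users: *r* × *c*
- over the FAS: *s* × *r* × *c*

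**One user, worked through (assumed values).** Take fasting glucose 110 mg/dL, endogenous insulin 6 µU/mL and injected insulin 6 µU/mL, so *r* = 0.5.

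- Endogenous insulin alone: 6 × 110 / 405 = 1.63
- As measured at baseline: 12 × 110 / 405 = 3.26
- After injected insulin halves: 9 × 110 / 405 = 2.44
- Apparent change: 2.44 / 3.26 − 1 = −25%, with resistance unchanged

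**Range, with injected insulin halved (*c* = −0.5).**

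| Injected share *r* | Users | FAS, *s* = 0.5 | FAS, *s* = 0.25 |
|---|---|---|---|
| 0 (complete washout) | 0% | 0% | 0% |
| 0.10 | −5% | −2.5% | −1.25% |
| 0.25 | −12.5% | −6.25% | −3.1% |
| 0.50 | −25% | −12.5% | −6.25% |

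A 25% fall in injected insulin gives half of each entry. A rise in dose gives the same sizes with the opposite sign.

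**Insulinogenic index.** The documents give no formula. If it is an early increment over the 0-minute value, a steady injected background *B* drops out of the insulin term: (I30 + B) − (I0 + B) = I30 − I0. Injected insulin could still affect the glucose term, but the index is less exposed than HOMA-IR, which carries *B* in full.

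**The case against.** The strongest reply is that the operative analysis is not in view. Protocol 12.3 describes itself as a summary of principal features, and SAP 8.5 places these biomarkers elsewhere. A one-line list entry without a split does not show that the final analysis lacks one. This stands: the point can be made only against the text as written, together with a request that the separate document deal with it.

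The second reply is that the effect is conditional. Withholding is to be counselled before every OGTT, each test follows a fast of at least 8 hours, non-fasting results are discarded, and insulin at entry is capped at 0.3 units/kg/day. If no injected insulin remains, or the assay does not detect it, the artefact is zero. This also stands. The documents give neither a withholding time nor the assay, so zero cannot be assumed or ruled out.

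A reader might infer three stronger things that the documents do not support:

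- **That the insulin results will be wrong, by about 25%.** The 25% is for users only, at the top of an assumed range. The corresponding FAS figure is 12.5%, and the range starts at 0%.
- **That the dose is expected to fall on treatment.** Change in dose is listed as an endpoint. No direction or expectation is stated.
- **That the main tables should therefore drop OGTTs with recent insulin.** That conditions on a post-baseline variable. A subject who stops injecting during the study would qualify at Week 48 but not at baseline, so would have no change value, and daily users would largely disappear. Such a restriction is suitable only as a labelled sensitivity summary.

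C-peptide is already in the same list, so the plan does have a secretion measure that injected insulin does not supply. What it lacks is a statement that conclusions on secretion in users will rest on it.

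**Conclusion.** The point holds as a risk in the plan as written. Protocol 12.3.3.5 pools users and non-users of insulin for measured insulin and two indices built on it, in a sample where about 30 of 60 may inject. Neither document states a split, a rule for recent insulin, or a use for the 24-hour record.

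The size cannot be fixed from the documents. With half the subjects on insulin and injected insulin halved, the spurious fall in mean HOMA-IR over the FAS is 0% to 12.5%, and 0% to 25% among users, for an injected share of 0% to 50%. This rests on residual injected insulin at sampling and an assay that detects it. Fasting insulin and HOMA-IR are the measures mainly exposed.

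These are descriptive "other" endpoints in the plan's own ranking. The primary and secondary efficacy endpoints use glucose, not measured insulin, so this mechanism does not reach them.

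**What to change.** In Protocol 12.3.3.5 and in the separate biomarker document:

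1. Present insulin, HOMA-IR and the insulinogenic index by baseline insulin use (the Yes/No item in SAP 8.2.2), and keep the all-FAS table beside them.
2. Add a sensitivity summary limited to subjects with no insulin recorded in the 24 hours before both the OGTT that supplies the baseline value and the post-baseline OGTT. Label it as a selected subset. It also catches subjects who start insulin on study, whom a baseline split misses.
3. State that conclusions about secretion in insulin users rest on C-peptide.
4. Give the formulas for the two indices and say whether the insulin assay detects injected insulin, so that readers can judge which measures are exposed.

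The cost is analysis wording and a few extra tables, mostly from data already collected. The drawbacks are smaller groups per table, a sensitivity subset selected on a post-baseline variable, and possibly no 24-hour record for any OGTT done before that record was added by amendment.
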